***Other Investigators:**

[name]
Department of Radiology
Brigham and Women's Hospital
[name]
Boston, MA 02115
Ph: [REDACTED]
Email: [contact]

[name]
Department of Radiation Oncology
Brigham and Women's Hospital
[name]
Boston, MA 02115
Phone: [REDACTED]
[contact]

[name]
Department of Radiation Oncology
Brigham and Women's Hospital
[name]

Boston, MA 02115
Phone: [REDACTED]
Email: [contact]

[name], PHD
Department of Radiology
Brigham and Women's Hospital
[name]
Boston, MA 02115
P: [REDACTED]
Email: [contact]

Statistician:

[name].
Brigham and Women's Hospital
Statistics Department
[name]
Boston, MA 02115
P: [REDACTED]
F: [REDACTED]
Email: [contact]

Study Coordinator and Data Manager:

[name]
Dana Farber Cancer Institute
Breast Oncology
[name]
Boston, MA 02215
P: [REDACTED]
F: [REDACTED]
Email: [contact]

Study Exempt from IND Requirements per 21 CFR 312.2(b).

Protocol Type / Version # / Version Date: Version #4, 11/08/2022
Original, Version #1, 5/25/2016

STUDY SCHEMA

Selection, Enrollment and Imaging:

Newly diagnosed breast cancer (stage I, II, III non-inflammatory) planning upfront surgery or neoadjuvant therapy (NAT)

↓
Patient informed consent obtained
Eligibility confirmed
Patient registered

↓
Pre-surgery or Pre-NAT MRI performed in routine prone position and investigational supine position

↓
Extent of disease/ lesions seen on MRI compared with other standard imaging modalities including mammogram and ultrasound

↓
If additional suspicious findings seen only on MRI a second-look US and/or additional mammographic views with or without biopsy will be performed using prone and supine MRI sequences for guidance

↓
Radiologist completes brief survey regarding usefulness of supine MRI for second-look US +/- biopsy (if applicable)

Patient proceeds with upfront surgery or NAT:

If receives NAT, post-NAT imaging obtained to include +/-mammogram, +/- US, + breast MRI prone+supine

Surgery:

↓
Per surgeon/radiologist preference, tumor localization (with wire or radio-seed) performed by radiologist prior to surgery

[figure not shown]

TABLE OF CONTENTS

1.1	Study Design and Hypotheses	7
1.2	Primary Objectives	8
1.3	Secondary Objectives	8
2.	BACKGROUND	9
2.1	Study Disease and Rationale	9
2.2	Correlative Studies Background	12
3.	PARTICIPANT SELECTION	12
3.1	Inclusion Criteria	12
3.2	Exclusion Criteria	13
3.3	Inclusion of Women and Minorities	13

1.1 Study Design and Hypotheses

This study is designed as a prospective Phase II trial aimed to determine the value of supine breast MRI for women newly diagnosed with stage I-III non-inflammatory breast cancer undergoing upfront surgery or neoadjuvant therapy (NAT).

We hypothesize that breast MRI with supine sequences will provide advanced image-based characteristics for (1) radiological procedures (2) surgical operations and (3) adjuvant radiation delivery, and further hypothesize that these images will allow for superior characterization and localization of breast lesions as compared to traditional imaging studies (mammography, ultrasound, prone MRI). This will be measured by a combination of qualitative (clinician surveys of supine MRI usefulness for radiologic and surgical procedures and for radiation treatment/delivery) and quantitative measures (correlation in residual tumor size estimation with the gold standard method, success rate of US-guided lesion identification and/or biopsy performed with supine MRI guidance, and rate of re-excisions for breast conserving surgical operations when supine MRI used for surgical planning).

More specifically, we hypothesize that:

- (1) Supine breast MRI will provide an accurate assessment of residual breast tumor size
- (2) Supine breast MRI will be superior to other imaging modalities in estimation of final tumor size as determined on post-operative pathology (gold standard).
- (3) Supine MRI will help radiologists identify suspected satellite lesions and/or additional suspicious findings during the second look ultrasound procedure. Tissue sampling under sonographic-guidance is more cost effective and patient centric for the patient compared to biopsy under MRI-guidance; therefore, the correlation of MRI findings with ultrasound findings is an important patient-centered endpoint.
- (4) Supine breast MRI will improve surgical planning efforts for breast conserving surgery by providing surgeons with more accurate information regarding the tumor's location within the breast in the supine position, which will translate into reduced re-excision rates associated with this procedure.
- (5) Supine breast MRI will improve adjuvant radiation therapy planning efforts following breast surgery by providing radiation oncologists with more accurate imaging information of the patient in the supine position, allowing for potentially improved radiation delivery

A total of 74 patients will be recruited to participate in this study. Enrolled patients will undergo upfront surgery or receive a NAT regimen at the discretion of the treatment team. All patients will have their breast tumor evaluated with standard imaging to include mammography, 2D and/or 3D, ultrasound, prone contrast-enhanced MRI and investigational supine contrast-enhanced MRI sequence pre-surgery. For patients planning for NAT, we will also attempt to obtain a prone contrast-enhanced MRI and investigational supine contrast-enhanced MRI sequence pre-NAT; however if a patient presents with an outside pre NAT MRI this will not be repeated. The tumor's position on all imaging modalities will be registered, and tumor location between supine and prone MRI sequences will be determined. Investigational supine MRI images will be provided to radiologists and surgeons for purposes of performing additional imaging interventions, if they are deemed necessary by the treatment team, and for surgical

planning. Estimates of tumor size pre-operatively as identified by each imaging modality will be compared to final pathology, allowing the correlation of each imaging modality for estimating residual tumor size with the gold standard method (pathology).

For patients undergoing BCT, the prone and supine MRI images will be registered in the image-processing software, 3D Slicer, and the segmented tumor models will be overlaid on the images. Screenshots showing the displacement of the tumor from the prone to the supine images will be provided to the surgeon to plan the tumor resection. Following completion of the operation a survey of the breast surgeon will be administered to determine their perceived usefulness of the supine imaging for surgical planning. Volume of excised tissue, rates of positive margins, and the need for reoperation, will be recorded, and these measures (using supine MRI imaging) will be compared to historical data to determine the impact of supine MRI imaging on surgical outcomes.

Patients requiring postoperative radiation therapy will be referred to radiation oncology post-operatively. Supine MRI images obtained prior to surgery will be provided to the radiation oncologists for breast treatment planning. A survey will then be administered to the attending treating radiation oncologist to assess the usefulness of supine MRI for treatment planning.

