9. STATISTICAL CONSIDERATIONS

This is a phase II study aimed at evaluating the ability of breast MRI (prone and supine) to accurately estimate breast tumor size (in term of correlation with gold standard size on post-operative pathology analysis). This study is also designed to compare correlation between supine

breast MRI with existing imaging modalities at estimating tumor size. Finally, this study is designed to characterize the changes occurring in breast tumor-associated properties/dimensions between the prone and supine imaging position and to determine the correlation of tumor location and geometry on pre-surgical supine MRI and prone MRI. A total of 80 patients will be recruited to participate in this study.

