9.2 Sample Size, Accrual Rate and Study Duration

For the primary outcome, with 73 eligible patients we will have 90% power to detect a correlation coefficient between pre-surgical prone or supine MRI and tumor size of 0.85 from 0.70 with a two-sided one sample z-test at $\alpha=0.05$ level.

With 73 eligible patients, we will also have more than 80% power to detect a difference in correlation from 0.85 between the supine MRI and the pathology tumor size and 0.70 between the standard imaging and the pathology tumor size with a two-sided two sample z-test at $\alpha=0.05$ level, assuming the correlation between the supine MRI and the standard imaging is 0.70.

Assuming the dropout rate will be 10%, we will plan to accrue a total of 80 patients. With an anticipated enrollment of 5 patients per month, accrual should be completed in approximately 16 months.

The below table “Accrual Targets” reflects the accrual targets anticipated for this study. As noted in detail in Section 3.3, men are not likely candidates for breast conserving surgery, and are not eligible for this trial. Approximately 10% of the target enrollment will be Hispanic or African American.

Accrual Targets					
Ethnic Category	Sex/Gender				
	Females	+	Males	=	Total
Hispanic or Latino	8	+	0	=	8
Not Hispanic or Latino	72	+	0	=	72
Ethnic Category: Total of all subjects	80 (A1)	+	0 (B1)	=	80 (C1)
Racial Category					
American Indian or Alaskan Native	1	+	0	=	1
Asian	4	+	0	=	4
Black or African American	12	+	0	=	12
Native Hawaiian or other Pacific Islander	0	+	0	=	
White	63	+	0	=	63
Racial Category: Total of all subjects	80 (A2)	+	0 (B2)	=	80 (C2)

(A1 = A2)

(B1 = B2)

(C1 = C2)

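### Section 1.1 gives the recruitment total as 74; Section 9, Section 9.2 and the accrual table give 80, and the stated accrual rate and duration imply 80.

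*Combined protocol and SAP*

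**What the plan says.** Section 1.1 (Study Design and Hypotheses) describes the design and gives the enrolment total: "A total of 74 patients will be recruited to participate in this study". The opening paragraph of Section 9 (Statistical Considerations) uses the same sentence with another number: "A total of 80 patients will be recruited to participate in this study".

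Section 9.2 (Sample Size, Accrual Rate and Study Duration) shows where the larger figure comes from. It bases the primary outcome on an evaluable number: "with 73 eligible patients we will have 90% power", for a correlation with pathologic "tumor size of 0.85 from 0.70", tested two-sided at 0.05. It then allows for losses: "Assuming the dropout rate will be 10%, we will plan to accrue a total of 80 patients". The timeline follows: "With an anticipated enrollment of 5 patients per month, accrual should be completed in approximately 16 months". The accrual table in the same section totals 80 by ethnicity and 80 by race.

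No section explains the 74 or describes it as anything other than the number to be recruited.

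**The concern.** The two sentences differ only in the number, so they cannot both be right. Neither comes from an amendment log or a summary of changes.

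The recruitment total determines when accrual stops, and it is the natural reference when the monitoring committee reviews accrual under Section 8.2. Section 1.1 is the design summary, where many readers look first. Someone working from it would close accrual 6 patients early.

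The 74 also leaves almost no room for losses that the protocol itself expects. Section 5.5 takes patients off study if they cannot complete the supine MRI, do not get a pre-surgical MRI, or have surgery elsewhere. Section 9.7 excludes patients with uninterpretable MRI, or with surgery elsewhere, from the primary analysis. Section 9.2 sets the allowance for dropout at 10%.

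**Working it through.** **Inputs.** All are from Section 9.2 except the 74, which is from Section 1.1: alternative correlation 0.85, null correlation 0.70, two-sided alpha 0.05, power 90%, 73 eligible patients, 10% dropout, 5 patients a month, about 16 months, and a correlation of 0.70 between supine MRI and standard imaging for the second comparison.

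**Step 1: reproduce the plan's evaluable number.** For a one-sample Fisher z-test,

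n = ((z for 0.975 + z for 0.90) / (atanh 0.85 − atanh 0.70))² + 3.

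The difference on the Fisher scale is 1.2562 − 0.8673 = 0.3889. The normal quantiles sum to 1.960 + 1.282 = 3.242. This gives n = 72.49, rounded up to 73. Power at 73 is 90.2%. The stated 73 and 90% reproduce.

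**Step 2: check the enrolment total against dropout.** Dividing by the retained fraction, 73 / 0.9 = 81.1, or 82 when rounded up. The unrounded requirement gives 72.49 / 0.9 = 80.5. The cruder multiplication gives 73 × 1.1 = 80.3. The stated 80 is within rounding distance of these figures. The 74 is not: it tolerates a loss of 1 − 73/74 = 1.4%, against the 10% assumed.

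**Step 3: check the other places that carry the total.**

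- Ethnicity rows: 8 + 72 = 80.
- Race rows: 1 + 4 + 12 + 63 = 80.
- Timeline: 5 × 16 = 80. A total of 74 would take 74 / 5 = 14.8 months.

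**Step 4: consequence for power.** Evaluable patients after 10% dropout are 74 × 0.9 = 66.6 (66 to 67) or 80 × 0.9 = 72. One-sample power is Φ(0.3889 × √(n − 3) − 1.960). For the second comparison, power was computed with three standard z-tests for dependent correlations (Meng–Rosenthal–Rubin, Dunn–Clark and Steiger); the range across the three is shown.

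| Scenario | Evaluable n | First primary test (0.85 vs 0.70) | Supine vs standard imaging |
|---|---|---|---|
| Section 9.2 as stated | 73 | 90.2% | 85.2% to 85.9% |
| 80 recruited, 10% dropout | 72 | 89.8% | 84.7% to 85.4% |
| 74 recruited, 10% dropout | 66 | 87.0% | 81.4% to 82.1% |
| 74 recruited, 10% dropout | 67 | 87.5% | 82.0% to 82.7% |

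The claim of more than 80% power for the second comparison survives at either total. The 90% claim for the first holds to rounding with 80 recruited and does not hold with 74.

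**The case against.** The strongest reply is that this is a clerical slip with little effect. Section 9 governs sample size and is consistent on the total, and the correction is one number that changes no analysis. The power at stake is 2 to 3 percentage points on one test. The plan's own 80 is itself a fraction under 90% once 10% dropout is applied, and with no more than one loss 74 would still deliver 73 evaluable patients. The timeline never prints 80, and since it is only approximate, 14.8 months is not strictly ruled out. The reason for the 74 is unknown, so choosing 80 is an inference.

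Much of this stands as a limit on size. The power loss is modest, the timeline supports 80 without proving it, and the direction of the fix is an inference, although everything visible in the document points the same way. None of it removes the contradiction. The 74 cannot be read as an evaluable count, because Section 9.2 gives that as 73 and Section 1.1 speaks of recruitment. Meeting 90% power with 74 recruited would require setting aside the plan's own dropout assumption. A total sample size is a figure the trial is run on, so a wrong value is more than a typing matter even when the cure is simple.

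**Conclusion.** The contradiction is real, and 74 is the outlier. The gap is 6 patients, or 6 / 80 = 7.5% of the planned total. Taken at face value with 10% dropout, 74 lowers power for the first primary test from the stated 90% to between 87.0% and 87.5%. Eighty is adequate as planned, and no increase in enrolment is called for.

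These power figures rest on Section 9.2's assumptions: a true correlation of 0.85, a null of 0.70, two-sided 0.05 and 10% dropout. Section 9.5 names a null of 0.6 for the same test; against that value power is about 99% even with 66 patients. That mismatch is a separate inconsistency and does not bear on which recruitment total is right. The conclusion that the protocol states two totals depends on none of these assumptions.

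**What to change.** In Section 1.1, change the recruitment total from 74 to 80 so that it agrees with Section 9, Section 9.2 and the accrual table. The cost is one number; the Section 9 enrolment target, timeline, analysis and stated power stay as they are.

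If the sponsor did intend 74, the correction runs the other way and is larger: Section 9, the accrual table, the timeline, and the dropout and power statements in Section 9.2 would all have to be reworked and justified.

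An optional small addition to Section 9.2 would say that 80 recruited with 10% dropout gives about 72 evaluable patients, since strict inflation of 73 gives 82. This is a matter of transparency only.

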1.2 Primary Objectives

The primary objectives are:

- 1) Determine the Pearson correlation between pre-operative prone and supine MRI for estimating tumor size as compared to the gold standard of pathologic evaluation of the surgical specimen.
- 2) To compare the Pearson correlation between pre-surgical standard imaging (mammography, ultrasound, prone MRI) and the gold standard of pathologic evaluation of the surgical specimen and the Pearson correlation between pre-surgical supine MRI and gold standard of pathologic evaluation of the surgical specimen for the evaluation of tumor size.
- 3) To explore the potential changes occurring in tumor-associated properties/dimensions between the prone and supine imaging position and to determine the correlation of tumor location and geometry on pre-surgical supine MRI with prone MRI. Tumor location will be assessed in terms of distance from nipple, chest wall, and skin. Tumor geometry will be assessed on multiple properties including volume, surface area, diameter, sphericity, and compactness. Patients with both pre-NAT and pre-surgical MRI will also be evaluated for the pre-NAT prone/supine MRI and pre-surgical prone/supine MRI comparison.

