In the upfront surgery setting, the use of Breast MRI has been shown to compliment traditional

imaging modalities (MMG/US) for determining extent of disease; however there remains a problem with over-estimation of lesion size. This combined with the frequency of identification of second lesions which require biopsy (and are often not visible on MMG/US) has been shown to correlate with increased use of mastectomy, with patients often deferring biopsy altogether. Whether or not supine MRI can improve upon correlation with tumor size in the upfront surgery setting and whether or not supine MRI can lead to improved identification of second lesions requiring biopsy has not been tested.

In the NAT setting, breast MRI has demonstrated higher accuracy over physical examination, mammography, and targeted breast ultrasound in the evaluation of tumor response to NAT and prediction of amount of residual disease. [12, 20-28]. The correlation of residual tumor size following NAT and histopathology in patients who underwent prone MRI before BCS has been reported to be approximately $r=0.7$ (Bhattacharyya et al ($r=0.71$), Rosen et al ($r=0.75$), Martincich et al ($r=0.72$), Segara et al ($r=0.75$)[12, 27-29]. For patients who require NAT for downstaging to BCT, repeating the MRI after NAT (pre-surgery) is standard for surgical treatment planning. In practice, it is uncommon to exclusively rely on a single imaging modality for breast cancer evaluation, and newly diagnosed breast cancer patients routinely have diagnostic mammography and ultrasound imaging as well. In patients undergoing NAT, these images are also repeated after NAT (pre-surgery) for surgical treatment planning.

One of the challenges inherent with the current breast MRI design is that the images are obtained with the patient in the prone position. Tumors are displayed to both radiologists and surgeons in relation to their position in the prone breast, however both ultrasound and surgery are performed on the supine breast. The changes in breast position- especially for patients with large or pliable breasts- can significantly displace breast tumors, making it difficult for radiologists to correlate MRI and sonographic findings, and for surgeons to localize tumors intraoperatively[33, 34].

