Limitations of other modalities are numerous. For example, NAT can induce unpredictable fibrous changes that can reduce the reliability of clinical examination. Certain breast cancer subtypes, such as lobular carcinoma for example, are difficult to visualize mammographically and can increase in firmness after NAT, causing an initially occult lesion to become more clinically palpable with treatment[30]. Assessment of tumor size on exam and with mammography can be undermined by the infiltrative nature of locally advanced breast cancers, especially in the setting of dense breast tissue [25, 26, 31]. Suspicious microcalcifications initially noted on mammogram may persist, become coarser, or occasionally increase on mammograms after NAT. Peintinger et al demonstrated that a combination of mammogram and ultrasound could provide moderate agreement in predicting residual tumor size after NAT; however, the correlation and agreement with pathologic residual tumor size was underestimated for lobular carcinoma and overestimated for poorly differentiated tumors [32]. Yeh et al also demonstrated similar findings when comparing agreement regarding the rate of response between clinical examination, mammography, sonography, and MRI with pathology as the reference standard, with agreement rates of 19%, 26%, 35%, and 71%, respectively [26]. Although MRI was noted to be the superior modality in this study, it was not without its own limitations; MRI was felt to both underestimate and overestimate residual tumor measurements, leaving clinicians with an ongoing need for an improved way to monitor the response to and the disease remaining after NAT regimens.

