A secondary objective of a Phase I Clinical Trial we recently completed at our institution evaluating the feasibility of intraoperative breast MRI was to better characterize the positional change that occurs between the prone and supine imaged breast [30, 33, 34]. Our results, presented in 2015 at the Society of Breast Imaging Annual Meeting and at the New England Surgical Society Annual Meeting, showed that substantial tumor displacement occurs when the breast changes from the prone to the supine position, with an average tumor displacement of over 6cm [43, 44]. Additionally, we found substantial tumor deformation occurring between positions, with an average change in the measured volume of 23.8%, surface area of 6.5%, compactness of 16.2% and maximum 3D diameter of 7.1% (mean change from prone to supine imaging (as a percentage of the prone metrics) [34, 43]. This was unanticipated, as breast cancers have been shown to be more stiff than surrounding breast parenchyma (Krouskop et al showed stiffness of normal fat, normal glandular tissue, and invasive ductal carcinomas to be 20 kPa, 57 kPa, and 490 kPa, respectively) and thus deformation was suspected to be negligible [43, 45]. These deformations and displacements were visually represented on ‘composite’ MRI images, which simultaneously displayed a tumor’s location/shape using “3D tumor models” in both the prone and supine position (tumors were registered, and prone and supine MRI were overlaid), enabling surgeons and radiologists alike to visually identify each tumor’s location/size/shape in both orientations. Briefly, this was achieved by rigidly registering breast tumors on both post-contrast MRI series on thoracic cavities using the Mutual Information criterion, following initial alignment of the pulmonary veins [46-48]. 3D tumor models were then created in 3D Slicer by segmenting the tumors on the supine and prone MRIs using semi-automatic threshold-based algorithms on the subtracted images computed from the first post- and pre-contrast volumes, which were then further registered using Iterative Closest Point registration [48]. These tumor models, and their associated prone and MRI scans, were overlaid to generate the composite models presented to surgeons prior to surgery. Anecdotally, we found that these composite images were viewed as useful by both radiologists and surgeons alike, in assisting with tumor localization and with surgical planning. Based on these results, our institution adopted a policy

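### Accuracy and superiority of tumour sizing against pathology are judged only by Pearson correlation, which cannot show over- or under-sizing

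*Combined protocol and SAP*

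**What the plan says.** Section 1.1 sets out two hypotheses about size: "Supine breast MRI will provide an accurate assessment of residual breast tumor size", and "Supine breast MRI will be superior to other imaging modalities in estimation of final tumor size" as found on post-operative pathology. It adds that "Estimates of tumor size pre-operatively as identified by each imaging modality will be compared to final pathology", but the only product it names for that comparison is a correlation for each modality.

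Section 1.2 turns these hypotheses into correlations. Objective 1 reads "Determine the Pearson correlation between pre-operative prone and supine MRI for estimating tumor size as compared to the gold standard" of surgical pathology. Objective 2 compares the Pearson correlation for supine MRI with that for standard imaging. The introduction to Section 9 treats the two ideas as one, since the aim is to "accurately estimate breast tumor size (in term of correlation with gold standard size on post-operative pathology analysis".

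Sections 9.1 and 9.2 define and size the primary endpoint by correlation. Section 9.5 plans r with a 95% confidence interval, one-sample z-tests on r, and a z-test for correlated correlations. Its only paired-difference test, under objective 3, compares supine with prone MRI. The secondary analyses in Section 9.6 contain no size comparison with pathology.

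**The concern.** Accuracy and superiority in estimating size are claims about how close the imaging size lies to the pathologic size. Pearson r measures how tightly the points follow some straight line, whatever its intercept and positive slope. A modality that adds 1 cm to every tumour, or enlarges each by 30%, keeps exactly the same r.

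These are the errors that the protocol's own rationale describes. For upfront surgery, Section 2.1 says of MRI that "there remains a problem with over-estimation of lesion size". After neoadjuvant therapy it reports that "MRI was felt to both underestimate and overestimate residual tumor measurements".

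If the plan stays as it is, a high r, or a higher r for supine MRI, supports a statement about strength of linear association and nothing more. Objective 3 may show that supine sizes differ from prone sizes. No planned analysis would then say whether the shift corrects over-estimation or introduces under-estimation.

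**Working it through.** **The plan's own power figures (Section 9.2).** Inputs: n = 73, r = 0.85 against 0.70, two-sided alpha 0.05. With the Fisher transformation,

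power = Φ(√(n−3) × [atanh 0.85 − atanh 0.70] − 1.96) = Φ(8.367 × 0.389 − 1.96) = 90.2%.

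This reproduces the stated 90%. For the comparison of correlated correlations, with 0.70 between supine MRI and standard imaging, three standard z-tests give 85.2% to 85.9%, which agrees with the stated figure of more than 80%. The sizing is right for the tests it describes. The difficulty is what those tests measure.

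**Invariance.** If imaging size is replaced by c × size + d with c > 0, r is unchanged. This is algebra and needs no assumption.

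**Illustration.** The documents give no mean or SD for pathologic size, so I assume m = 2.0 cm and s = 1.2 cm. The imaging size is given the same mean and SD and is then multiplied by k.

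- Bias = m(k − 1)
- RMSE = √(s² + k²s² − 2rks² + bias²)
- Lin's concordance (CCC) = 2rks² / (s² + k²s² + bias²)

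| r | k | Bias (cm) | RMSE (cm) | CCC |
|---|---|---|---|---|
| 0.85 | 1.000 | 0 | 0.657 | 0.850 |
| 0.85 | 1.071 | +0.14 | 0.700 | 0.843 |
| 0.85 | 1.300 | +0.60 | 1.025 | 0.752 |
| 0.70 | 1.000 | 0 | 0.930 | 0.700 |
| 0.70 | 1.300 | +0.60 | 1.270 | 0.619 |

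Third row worked out: RMSE = √(1.44 × [1 + 1.69 − 2.21] + 0.36) = √1.051 = 1.025 cm.

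A modality with r = 0.85 loses its lead over an unbiased one with r = 0.70 at k = 1.245 on RMSE and at k = 1.398 on CCC. For an assumed SD of 0.8 to 1.5 cm, the crossings range from 1.18 to 1.28 and from 1.27 to 1.48. With a mean of 2.5 cm and SD of 1.5 cm instead, 30% over-sizing gives RMSE 1.28 cm against 1.16 cm for the unbiased comparator, so the picture is the same.

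**What the pilot suggests.** Section 2.1 reports an average prone-to-supine change in "maximum 3D diameter of 7.1" per cent, with no direction stated. Over-sizing of that amount (second row) barely moves RMSE or CCC.

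**What objective 3 cannot separate.** Take two cases for bias against pathology:

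- Prone +0.3 cm, supine 0: supine minus prone = 0 − 0.3 = −0.3 cm.
- Prone 0, supine −0.3 cm: supine minus prone = −0.3 − 0 = −0.3 cm.

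The correlations and the supine-minus-prone mean are identical. Supine RMSE is 0.657 cm in the first case and √(0.432 + 0.09) = 0.722 cm in the second. No planned analysis tells them apart.

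**Would 73 patients be enough?** The 95% half-width for mean bias is 1.993 × SD of differences / √73. For supine MRI (SD 0.657 cm) it is 0.153 cm, and for an r = 0.70 modality (SD 0.930 cm) it is 0.217 cm. A bias of 0.3 cm could be distinguished from zero in either.

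**The case against.** The strongest reply is that correlation was chosen openly. Section 1.1 says, before listing the hypotheses, that size estimation will be measured by correlation with the gold standard. The benchmarks in Section 2.1 are themselves correlations of 0.71 to 0.75. Objectives 1 and 2 ask for Pearson coefficients and will get them. This is a good reason to keep r, but it does not make r answer hypotheses 1 and 2.

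Second, the reversal above sets a biased supine MRI against an unbiased comparator, while the background attributes mis-sizing to prone MRI and to mammography with ultrasound as well. This is fair. If both over-size by 30%, supine MRI keeps its lead (RMSE 1.025 against 1.270 cm; CCC 0.752 against 0.619). The reversal is possible, not predicted.

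Third, the planned comparison of correlations does say something about closeness, because it reflects scatter about a line. That stands too. What goes unseen is systematic offset and scale error.

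Fourth, the data are less complete than they look. After neoadjuvant therapy, mammography and ultrasound are done as deemed necessary, and sizes are recorded only without radiographic complete response (Section 5.2.2). Differences also need the same dimension on imaging and pathology, and limits of agreement can mislead if error grows with tumour size. The first two limits weaken the Pearson analysis equally, and all of them bear on how the addition is reported. They also mean that fewer than 73 pairs may be available, so the half-widths above may be optimistic.

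**Conclusion.** The concern holds. Every planned comparison of imaging size with pathology is a correlation, and the hypotheses of accuracy and superiority would be answered only in part. That conclusion rests on the invariance of r and on the text of Sections 1.1, 1.2 and 9, and needs no assumed figure.

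The possible size of the effect depends on the assumed mean and SD. With 2.0 and 1.2 cm, about 25% over-sizing would reverse the ranking on RMSE and about 40% on CCC, against an unbiased comparator. The pilot change of 7.1% lies well below both. The correlation tests and their power remain valid. This is therefore a change the sponsor should make to support the intended claims; it is not a flaw that invalidates the trial.

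**What to change.** In Section 9.5, keep the Pearson tests and add one paragraph covering the following.

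- For supine MRI, prone MRI, mammography and ultrasound: the mean imaging-minus-pathology size difference with 95% CI, Bland-Altman 95% limits of agreement, and Lin's concordance coefficient.
- For supine MRI against each standard modality: a paired comparison of absolute error, |imaging − pathology|, in patients with both measurements. Give n for each comparison, since ultrasound is not required (Section 3.1.2).
- The same size dimension and the same handling of complete responses as in the Pearson analysis, both stated in the plan.
- A statement that these are estimates supporting objectives 1 and 2, not extra pass/fail criteria, and that a correlation result alone supports a claim about strength of linear association, not about accuracy or superiority in sizing.

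The cost is one paragraph and one results table, using sizes that Section 1.1 already plans to compare with pathology. There are no extra patients or scans, and the sample size is unchanged. The sponsor gives up the option of resting an accuracy claim on a high r alone.
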